#### 3.0 Patient Selection:

3.1 All patients must be willing and capable to provide informed consent to participate in the protocol.

- 3.2 Histologic confirmation of cancer will be required by biopsy, prior surgery, and re-biopsy at the discretion of the treating physician.
- 3.3 The patient's Zubrod performance status must be 0-2
- 3.4 Patients must be or have been ambulatory within a week prior to treatment.
- 3.5 Patients with instability of the spine requiring instrumentation as judged by a neurosurgeon are not eligible.
- 3.6 No planned systemic treatment is allowed within one week after treatment.
- 3.7 Patients must have localized spinal metastasis. This includes patients with a solitary lesion, a lesion that spans two contiguous levels, a lesion with a para-spinal component, and up to three separate single vertebral levels.
- 3.8 Patients with loss of normal vertebral height, due to for example compression fracture or other process, prior to treatment are not allowed. Patients with normal height and compression fracture are allowed.
- 3.9 Patients with prior fractionated radiation to the treated site are allowed. Their prior treatment plan with date, fractionation, dose and treatment fields must be obtained. There must be at least a three month interval elapsed from the prior radiation to the treated site and enrollment.
- 3.10 Patients must have had a visual analog scoring of pain  $\geq$ 4 at the planned treated site within 14 days of registration. Pain must be ongoing or require narcotic pain medicine to control.
- 3.11 Narcotic pain prescription and usage information must be available and documented.
- 3.12 Radiation sensitive histology such as lymphoma, myoloma, or plasmacytoma are not allowed.
- 3.13 Patients must be past their 18th birthday at time of registration.
- 3.14 Women of childbearing age must have documentation of a negative pregnancy test and agreed that they or their partner use an effective contraceptive method such as condom/diaphragm and spermacidal foam, non-stainless-steel intrauterine device, or prescription birth control pills.
- 3.15 Patients should not have a history of significant psychiatric illness.
- 3.16 Patients should not have severe, active co-morbidity that would preclude vertebroplasty or stereotactic radiotherapy, defined as follows:

3.16.1 Unstable angina and/or congestive heart failure requiring hospitalization within the last 6 months.

3.16.2 Transmural myocardial infarction within the last 6 months.

3.16.3 Acute bacterial or fungal infection requiring intravenous antibiotics at the time of registration.

3.16.4 Hepatic insufficiency resulting in clinical jaundice and/or coagulation defects.

3.17 Laboratory entry criteria:

3.17.1 PT within normal limits or planned and feasible to be corrected to normal limits prior to vertebroplasy.

3.17.2 PTT within normal limits or planned and feasible to be corrected to normal limits prior to vertebroplasy.

3.17.3 Platelet count must be  $\geq$  50,000.

3.18 Patient with epidural, spinal nerve, and/or cord compression on MRI may be included.

## 4.0 Pretreatment Evaluations / Management:

Note: This section lists baseline evaluations needed before the initiation of protocol treatment that do not affect eligibility.

4.1 Required Evaluations/Management

4.1.1 History and physical exam to include: determination and description of pain from spine metastasis and full neurological exam, VAS for given painful area, BPI, FACT-G, and EQ-5D.

- 4.1.2 Zubrod performance status (Appendix III).
- 4.1.3 Imaging studies to include: complete spine MRI and plain radiographs of involved areas
- 4.1.4 Laboratory work to include: complete blood count with platelets and differential within 30 days or after last round of chemotherapy, Electrolytes, BUN and creatinine as appropriate for histology
- 4.2 Highly Recommended Evaluations/Management
  - 4.2.1 Dedicated spine CT if clinically indicated or radiographic correlation is needed to evaluate the vertebral body cortex and look for bone fragments within the spinal canal.

## **5.0 REGISTRATION PROCEDURES**

- 5.1.1 Preregistration Requirements for diagnostic pathology review There are no requirements for central review of pathology used for initial diagnosis.
- 5.1.2 Pre-Registration Requirements for SBRT Treatment Approach In order to utilize SBRT in this protocol, the institution must have met technology requirements and have provided a description of techniques, methods, training, and experience showing competency to the study PIs.

## 5.2 Registration

5.2.1 Fax Registration

Prior to registration, participating investigators and institutions should review the eligibility checklist and confirm eligibility. Patients can be registered only after eligibility criteria are met. To register a patient, the site should fax the Enrollment Form to the Project Manager ([contact]). A unique, participant ID number will then be assigned.

## 5.3 Accreditation

5.3.1 Institutional Processes

Prior to treating patients on protocol, the institution's specific methods for immobilization (e.g., frame vs. frameless), targeting, dose construction, daily verification of accuracy, ongoing assessment of accuracy and Quality Assurance policies must be described to and approved by the study PI and other approved institutional PIs. The primary purpose of accreditation will be to insure that dose is delivered to the targets and avoiding normal tissues according to protocol criteria. This accreditation may be assessed by written documentation, conference calls, or direct observation via site visits. Additional data may be required of institutions to verify that techniques are performing as intended.

## 6.0 RADIATION THERAPY

## 6.1 DOSE SPECIFICATIONS

- 6.1.1 Stereotactic Targeting and Treatment
  - The term "stereotactic" for the purposes of this protocol implies the targeting, planning, and directing of therapy using beams of radiation along any trajectory in 3-D space guided by one or several fiducials of known 3-D coordinates. This differs from conventional radiation therapy in which therapy is directed toward skin marks or bony landmarks and assumed to correlate to the actual tumor target based on a historical simulation. It should be understood that Stereotactic Body Radiation Therapy (SBRT) has become a treatment that is well beyond just stereotactic targeting. Indeed SBRT is mostly about ablative range dose per fraction, accounting properly for errors including motion, careful construction of dosimetry that delivers high dose to the tumor and not normal tissues, and extra careful treatment delivery. This protocol will require treatments to be conducted with the use of a fixed 3-D coordinate system defined by fiducials. The coordinate system defined by the fiducials

should be directly related to the radiation producing device (e.g., couch and gantry) in a reproducible and secure fashion. Capability should exist to define the position of targets within the patient according to this same 3-D coordinate system. As such, the patient is set up for each treatment with the intention of directing the radiation toward a target according to the known 3-D coordinates as determined in the process of treatment planning. The nature of the fiducials themselves may include radio-opaque markers or rods placed at known locations in a frame or fixed structure adjacent to the patient as well as use of the tumor/spine itself as a fiducial (e.g. acquiring tomographic views of the tumor simultaneously with the treatment).

6.1.2 Dose Fractionation

Patients will be treated by two different dose fractionation schedules decided by a prior history of radiation to the treated area. Patients with no prior treatment will receive a single fraction of radiation. Each patient will have two target volumes of interest regardless of fractionation, a Planning Treatment Volume (PTV) and a Gross Tumor Volume (GTV) defined below. Minimum prescription dose for the single fraction treatment will be 14 Gy to at least 95% of the PTV and 20 Gy to at least 90% of the GTV. The plans overall maximum dose must occur within the GTV and be no greater than 25 Gy. For the single dose regimen, the spinal cord will receive no greater than 14 Gy to a point, 10 Gy to no more than 0.25 cc of spinal cord volume, and 7 Gy to no more than 0.5 cc of spinal cord volume. Patients with prior radiation treatment will be treated with 5 fractions of radiation. A minimum of 14 hours and a maximum of 7 days should separate each treatment. Minimum prescription dose for the five fraction treatment will be 2.8 Gy per fraction to at least 95% of the PTV for a total dose of 14 Gy and 4 Gy per fraction to at least 90% of the GTV for a total dose of 20 Gy. The plan's overall maximum dose must occur within the GTV and be no greater than 5 Gy per fraction for a total dose of 25 Gy. For the five fraction retreatment regimen, the spinal cord will receive no greater than 14 Gy (2.8 Gy per fraction) to a point, 10 Gy (2 Gy per fraction) to no more than 0.25 cc of spinal cord volume, and 7 Gy (1.4 Gy per fraction) to no more than 0.5 cc of spinal cord volume. Treatment dose will prescribed typically to the 70-90 percent isodose line for each fractionation scheme.

Structure	Dose	Required Volume	Minor Volume Variation	Major Volume Variation	Required Conformality index (CI)
PTV	≥14 Gy	$\geq$ 95%	90% - 95%	< 90%	1.3
F I V	≥ 12.6 Gy	$\geq$ 99%	95% - 99%	< 95%	
GTV	20 Gy	≥90%	85% - 90%	< 85%	

Total doses will be the same for the single fraction and five fraction treatments

#### 6.1.3 Premedications

Unless contraindicated, it is recommended but not required that all patients receive corticosteroid premedication (e.g. Decadron 4 mg p.o. in a single dose, or equivalent) 15-60 minutes prior to each of the five treatments for the intended purpose of modulating immediate acute inflammatory effects. Analgesic premedication to avoid general discomfort during long treatment durations is also recommended when appropriate.

6.1.4 Supportive medicines Are allowed as medically indicated.

#### **6.2 Technical Factors**

6.2.1 Physical Factors

Only photon (x-ray) beams produced by linear accelerators with photon energies 6-21 MV will be allowed. Cobalt-60 and charged particle beams (including electrons, protons, and heavier ions) are not allowed.

6.2.2 Dose Verification at Treatment

Personal dosimeter measurements (e.g. diode, TLD, etc.) may be obtained for surface dose verification for accessible beams as per institutional preference. This information is not required by the protocol.

#### 6.3 Localization, Simulation, and Immobilization

6.3.1 Patient Positioning

Patients will be positioned supine in a stable position capable of allowing accurate reproducibility of the target position from treatment to treatment. Positions uncomfortable for the patient should be avoided so as to prevent uncontrolled movement during treatments. A variety of immobilization systems may be utilized including stereotactic frames that surround the patient on three sides and large rigid pillows (conforming to patients external contours) with reference to the stereotactic coordinate system. All positioning systems must be validated and accredited by the Study Committee (Principal Investigator and Institutional PIs) prior to enrolling or treating patients on this trial. Patient immobilization must be reliable enough to insure that the Gross Tumor Volume (GTV) does not deviate beyond the confines of the Planning Treatment Volume (PTV) as defined in Section 6.4 with any significant probability (i.e., < 5%).

6.3.2 Inhibition of Effects of Internal Organ Motion

Special considerations must be made to account for the effect of internal organ motion (i.e., breathing, etc.) on target positioning and reproducibility. In some cases, the intrafractional tumor motion is small and no special maneuvers are required to achieve motion limits (as is true with most spinal metastasis treated in the supine position). Treating in the prone position will accentuate internal organ motion problems related to breathing and should be avoided unless special measures are taken to account for this motion. When accounting for intrafractional motion, acceptable maneuvers including accelerator beam gating or tracking with the respiratory cycle, and active breath-holding techniques. Internal organ inhibition maneuvers must be reliable enough to insure that the Gross Tumor Volume (GTV) does not deviate beyond the confines of the Planning Treatment Volume (PTV) as defined in Section 6.4 with any significant probability (i.e., < 5%). Assessment of this motion will be left to the institution. This type of interfractional motion analysis with correction is only required by protocol just prior to each separate treatment. Intrafraction assessment during the course of each treatment (dynamic and adaptive maneuvers) is allowed and encouraged especially if treatment times are long.

6.3.3 Localization and treatment maneuvers

A direct method of localization of the spine on the day of treatment must be used in this protocol. Acceptable methods would include placing a radio-opaque seed or marker that can be visualized and triangulated using dual imaging prior to simulation and planning. Also, it would be acceptable to perform computed tomography such as axial, spiral or conebeam CT prior to each treatment in the treatment position to identify the tumor target directly. Orthogonal kv or mv x-ray images (or patients should undergo a tomographic imaging study utilizing the linear accelerator couch, if available) should be obtained on the day of treatment and compared to digitally reconstructed images from simulation to ensure proper alignment.

#### **6.4 Treatment Planning/Target Volumes**

6.4.1 Image Acquisition

Computed Tomography (CT) will be the primary image platform for targeting and treatment planning. The planning CT scans must allow simultaneous view of the patient anatomy and fiducial system for stereotactic targeting. Treatment planning images should be performed in the treatment position using all aids/maneuvers described above. Axial acquisitions with gantry 0 degrees will be required with spacing  $\leq 2.0$  mm between scans. Images will be transferred to the treatment planning computers via direct lines, disc, or tape.

Image fusion with other imaging modalities such as MRI that might be useful in delineating the target and normal tissues is encouraged. MRI is to be done in the treatment position to allow for precise fusion.

#### 6.4.2 Target Volumes

The GTV (gross tumor volume) will be defined as gross tumor visualized on CT/MRI scan in the vertebral body, para-spinal recess, or in the spinal canal. The CTV (clinical target volume) will include the GTV and contiguous bone marrow cavity adjacent to the tumor. The posterior elements of the vertebra will be included in the CTV only when directly involved by gross tumor. GTV and CTV target volume will be outlined by an appropriately trained physician. The target will generally be drawn using CT soft tissue/bone windows and from fused MRI. Since the spine is very stable and daily image guidance is used there will be no expansion from CTV to PTV. That is, the CTV will also be the PTV (planned target volume).

#### 6.4.3 Dosimetry

Three-dimensional coplanar or non-coplanar beam, arc rotation, or Intensity Modulated Radiotherapy (IMRT) beam arrangements will be custom designed for each case to deliver highly conformal prescription dose distributions. Non-opposing, non-coplanar beams are preferable. Typically, 10-15 beams of radiation will be used with roughly equal weighting for conventional linac treatments. When static beams are used, a minimum of 10 nonopposing beams should be used. For arc rotation techniques, a minimum of 300 degrees (cumulative for all beams) should be utilized. For CyberKnife treatments many more beams may be utilized depending on the size and the location. For this protocol, the isocenter is defined as the common point of gantry and couch rotation for the treatment unit. Field aperture size and shape should correspond nearly identically to the projection of the PTV along a beam's eye view (i.e. no additional "margin" for dose build up at the edges of the blocks or MLC jaws beyond the PTV). As such, prescription lines covering the PTV will typically be the 70-90% line (rather than 95-100%); however, higher isodoses (hotspots) must be manipulated to occur within the target and not in adjacent normal tissue. The isocenter in stereotactic coordinates will be determined from system fiducials (or directly from the tumor) and translated to the treatment record.

The treatment dose plan will be made up of multiple static beams or arcs as described above. The plan should be normalized to a defined point corresponding closely to the center of mass of the GTV ( $COM_{GTV}$ ). Typically, this point will be the isocenter of the beam rotation; however, it is not a protocol requirement for this point to be the isocenter. Regardless, the point identified as  $COM_{GTV}$  must have defined stereotactic coordinates and receive 100% of the normalized dose. Because the beam apertures coincide nearly directly with the edge of the PTV (little or no added margin), the external border of the PTV will be covered by a lower isodose surface than usually used in conventional radiotherapy planning, typically around 80% but ranging from 70-90%. The prescription dose in both the single fraction and five fraction treatments will be delivered to the margin of the GTV and fulfill the

requirements below. As such, a "hot spot" will exist within the GTV centrally at the  $COM_{GTV}$  with a magnitude of the prescription dose times the reciprocal of the chosen prescription isodose line (i.e., 70-90%).

For purposes of dose planning and calculation of monitor units for actual treatment, all tissues within the body should be modeled in the planning system as to their electron density. Proper heterogeneity correction algorithms should be approved by the PI.

Successful treatment planning will require accomplishment of all of the following criteria:

- $\frac{1)}{\text{The treatment plan should be normalized such that 100\% corresponds to the center of mass of the GTV (COMGTV). This point will typically also correspond (but is not required to correspond) to the isocenter of the treatment beams.$
- 2) Prescription Isodose Surface Coverage The prescription isodose surface will be chosen such that ≥95% of the target volume (PTV) is covered by the minimum prescription isodose surface (see section 6.1.2) and 99% of the target volume (PTV) receives a minimum of 90% of the minimum prescription dose. However, the spinal tolerance limits in section 6.5 should not be exceeded, even if the goals of target coverage remain unmet. In such a case, the treatment should proceed at the attainable dose without exceeding spinal cord tolerance with a potential protocol violation for target coverage.
- 3) Target Dose Heterogeneity

The prescription isodose surface selected in number 2 (above) must be  $\geq 60\%$  of the dose at the center of mass of the GTV (COMGTV) and  $\leq 90\%$  of the dose at the center of mass of the GTV (COMGTV). The COMGTV corresponds to the normalization point (100%) of the plan as noted in 1) above.

- 4) High Dose Spillage
  - a. Location

Any dose greater than 105% of the prescription dose should occur primarily within the PTV itself and not within the normal tissues outside of the PTV. Therefore, the cumulative volume of all tissue outside of the PTV receiving a dose greater than 105% of prescription dose should be no more than 15% of the PTV volume. Ideally, these hot spots will be manipulated to occur within the gross tumor volume. IMRT and other techniques will be encouraged to accomplish this goal.

b. Volume

Conformality of PTV coverage will be judged such that the ratio of the volume of the prescription isodose meeting criteria 1) through 4) to the volume of the PTV is less than 1.3.

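### The term *prescription dose* has two meanings in the planning rules, and on neither does the whole 70-90% isodose range fit both the 20 Gy GTV goal and the 25 Gy maximum

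*Combined protocol and SAP*

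**What the plan says.** All references are to the combined protocol and SAP.

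- **6.1.2 Dose Fractionation** uses *minimum prescription dose* for two levels in the single-fraction group: "14 Gy to at least 95% of the PTV and 20 Gy to at least 90% of the GTV". It then caps the plan: "The plans overall maximum dose must occur within the GTV and be no greater than 25 Gy". The five-fraction group has the same totals, with a maximum "no greater than 5 Gy per fraction for a total dose of 25 Gy". On the isodose line it says: "Treatment dose will prescribed typically to the 70-90 percent isodose line for each fractionation scheme".
- **6.4.3 Dosimetry** places the prescription line at the PTV border, "typically around 80% but ranging from 70-90" per cent. It then says that the prescription dose "will be delivered to the margin of the GTV and fulfill the" requirements listed below it. The hot spot at the GTV centre of mass is given "with a magnitude of the prescription dose times the reciprocal of the chosen prescription isodose line (i.e., 70-90" per cent, this time with no qualifier such as typically.
- **6.4.3, criterion 2** ties the prescription surface to coverage of at least 95% of the PTV and refers back to 6.1.2.
- **6.4.3, criterion 3**: "The prescription isodose surface selected in number 2 (above) must be" at least 60% and at most 90% of the dose at the GTV centre of mass.
- **6.4.3, criterion 4** limits spillage above 105% of the prescription dose outside the PTV, and requires a ratio of prescription isodose volume to PTV volume below 1.3.
- **6.8.4 Target Coverage Compliance** uses the term for the PTV and, in the same paragraph, for the GTV.

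**The concern.** The hot-spot rule divides a dose by an isodose fraction. It cannot be applied until one knows which dose is meant, and the text supports two. Neither choice works over the whole stated range: one leaves the centre too cool for the GTV goal, and the other takes part of the range above the plan maximum.

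The spillage rule is expressed as a percentage of the same undefined dose. Section 6.4.3 makes all of its criteria conditions of a successful plan, and participating institutions plan their own cases. Two planners could therefore read the rule differently in good faith and judge the same plan differently. The first scheduled radiotherapy quality review (6.9) comes only after 9 single-fraction cases and 6 cases in the other group.

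**Working it through.** **Inputs.** From 6.1.2: PTV level 14 Gy, GTV level 20 Gy, maximum 25 Gy. From 6.4.3: isodose fraction 0.70 to 0.90 in the text and 0.60 to 0.90 in criterion 3; spillage factor 1.05. Section 6.4.3 gives no number for the GTV-margin dose, so 20 Gy is inferred from 6.1.2.

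**Reproducing the plan's own figures.** 0.90 × 14 = 12.6 Gy, which matches the second PTV row of the table in 6.1.2. Five-fraction totals: 5 × 2.8 = 14, 5 × 4 = 20 and 5 × 5 = 25 Gy, which also match. So for the PTV the prescribed dose is 14 Gy. For the GTV, 6.8.4 grades coverage by the prescription dose at 85-90% and below 85%; those are the bands of the 20 Gy row in the same table. Both meanings are in use.

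**Hot-spot formula.** Dose at GTV centre = prescription dose ÷ isodose fraction.

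| Isodose line | From 14 Gy | From 20 Gy |
|---|---|---|
| 60% (criterion 3 only) | 23.3 Gy | 33.3 Gy |
| 70% | 20.0 Gy | 28.6 Gy |
| 75% | 18.7 Gy | 26.7 Gy |
| 80% | 17.5 Gy | 25.0 Gy |
| 85% | 16.5 Gy | 23.5 Gy |
| 90% | 15.6 Gy | 22.2 Gy |

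**Reading A, exactly 14 Gy at the PTV.** Above the 70% line the centre is below 20 Gy, so the GTV goal would need most of the GTV to be hotter than its own hot spot. At 70% the centre is exactly 20 Gy, and 90% of the GTV would need at least the central dose.

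**Reading B, 20 Gy at the GTV margin.** The maximum is met when 20 ÷ f ≤ 25, that is f ≥ 0.80. Lines from 70% to just under 80% break it; lines from 80% to 90% satisfy both goal and maximum.

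**Text range against criterion 3.** The GTV goal and the maximum together put the centre between 20 and 25 Gy. The 14 Gy line then lies between 14 ÷ 25 = 56% and 14 ÷ 20 = 70% of the central dose. That is outside the text's 70-90% except at its edge, and below criterion 3's 60% once the centre exceeds 14 ÷ 0.60 = 23.3 Gy.

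**Can everything be met together?** Yes.

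- A 14 Gy surface at 60% to just under 70% gives a centre of 23.3 Gy down to just above 20.0 Gy, under the maximum. At 23.3 Gy the 20 Gy line is at 20 ÷ 23.3 = 85.7%.
- A PTV line above the 14 Gy floor also fits the text range: with a centre of 25 Gy, the 70% line is 17.5 Gy and the 80% line is 20 Gy.

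**Spillage threshold.** 1.05 × 14 = 14.7 Gy, or 1.05 × 20 = 21 Gy. On the second reading, tissue outside the PTV at 14.7 to 21 Gy does not count against the limit.

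**The case against.** The case on the other side has four parts.

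1. **14 Gy is a floor.** Section 6.1.2 calls it a minimum, its table gives at least 14 Gy, and section 1.2 speaks of 14-20 Gy. The results under Reading A apply only to a plan that sits exactly at the minimum. This stands.
2. **The range is soft, and criterion 3 is what binds.** In 6.1.2 and at the PTV border in 6.4.3, 70-90% is only typical; the mandatory limits are 60-90%. This stands as an answer to any claim that the limits are impossible. It does not remove the mismatch, since the hot-spot sentence repeats 70-90% unqualified.
3. **The criteria already identify the surface.** Criterion 2 ties it to the PTV, criterion 3 applies to that same surface, and the table in 6.1.2 lists the 1.3 conformality index on the 14 Gy PTV row. For the conformality index this stands: a reader might infer that its reference dose is also open, but the table points to the PTV line. For spillage it is weaker. That rule follows in a PTV-based sequence but names no dose, and the GTV-margin sentence comes shortly before the list.
4. **Little depends on the word.** Coverage is scored against explicit dose and volume rows, the maximum is in Gy, institutions' methods need prior approval (5.3.1), and quality reviews are scheduled (6.9). It stands that coverage and the maximum can be checked without settling the term. Spillage cannot.

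**Conclusion.** The point holds as a fault of definition and of mismatched ranges. *Prescription dose* means 14 Gy to the PTV in some places and the GTV-margin dose in others, and neither meaning fits the whole 70-90% range. At exactly 14 Gy, only the 70% edge brings the centre to 20 Gy. At 20 Gy, the range from 70% to just under 80% breaks the maximum and 80-90% does not. The text range of 70-90% differs from the 60-90% in criterion 3. The spillage threshold is 14.7 or 21 Gy depending on the meaning.

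Three stronger readings are tempting, and the documents do not support them:

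- A reader might infer that the dose limits contradict one another. They do not; the check above gives combinations that meet all of them.
- A reader might infer that no part of 70-90% works on either meaning. At 20 Gy, 80-90% does.
- A reader might infer that delivered dose will vary because of this wording. Minimum-dose rules, and the instruction to proceed at the attainable dose when cord limits bind, already allow variation, and nothing shows that the wording adds to it.

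The result rests on two assumptions: that the GTV-margin dose is 20 Gy, and that the GTV centre of mass is the hot spot, as 6.4.3 says. Sample size, alpha and power are unaffected. The correction should be made, because the ambiguity affects a normal-tissue planning rule and is cheap to remove.

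**What to change.** Reconcile 6.1.2, 6.4.3 (the GTV-margin sentence, the hot-spot sentence and criteria 2 to 4) and 6.8.4:

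- State which dose the word *prescription* refers to in the hot-spot sentence and in each of criteria 2, 3 and 4, including the 105% rule. For the conformality ratio, confirm in 6.4.3 what the table in 6.1.2 already indicates.
- Use distinct terms for the PTV level and the GTV level throughout.
- Make the isodose range in the text agree with criterion 3, and both agree with the GTV goal and the plan maximum.

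The study committee sets the values; no dose or isodose line is proposed here. The cost is protocol wording and re-issued planning criteria for the participating institutions.
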